4.2. Protocol Deviations

All deviations from the protocol are documented in the study file. In addition, deviations are reported to the Institutional Review Board as applicable.

Subject-specific deviations are recorded in the subject's source documents. The Sponsor will review all protocol deviations (PDs) on an ongoing basis and will be responsible for categorizing protocol deviations as exclusionary from IEP. Before the iDBL and the Final DBL, [REDACTED] will download the 'dv' csv file from Encapsia including all deviations entered in the system and will send it to the Sponsor. The Sponsor will use this source data to produce a classification Excel file by adding 2 new columns:

- IEPEXCL ("Leads to Exclusion from IEP?"). This column will be filled for each PD with:
 - o 'Yes' if the PD leads to exclusion of the subject from the IEP
 - o 'No' if the PD does not lead to exclusion of the subject from the IEP
- IEPEXCLREAS ("Reason for leading to exclusion from IEP"). This column will be filled for each row where IEPEXCL=Yes, with some categorical reasons of exclusions. Since prohibited medication/vaccine, immunogenicity samples taken out of window, and other major PDs will be recorded as PD and classified as exclusionary from IEP by the Sponsor, only the variable IEPEXCL will be used by [REDACTED] to identify subjects excluded from IEP.

The PD classification file will be finalized prior to iDBL for the Day 29 Analysis, and prior to the final DBL for the Final Analysis.

All PDs and their classification will be presented in a data listing.

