### 5.6.3 Immune Response Assessments

Serum antibody responses to pneumococcal polysaccharides induced by vaccination will be measured using 2 standard assays, OPA and multiplexed Meso Scale Discovery (MSD).

The OPA assay has been developed and qualified by Nexelis, a GCP-compliant central laboratory, to analyze the 24 polysaccharide antigens contained in VAX-24. The OPA assay has been consistently used as the method for measuring the functional capacity of pneumococcal antibodies, as antibodies to pneumococcal PS protect the host by opsonizing pneumococci (marking pneumococci for destruction) for phagocytosis (Burton and Nahm 2006).

The MSD assay has been developed and qualified by Nexelis to measure IgG responses against the 24 polysaccharide antigens contained in VAX-24. The MSD multiplex electrochemiluminescent assay is an immunoassay platform that allows simultaneous measurement of responses against multiple antigens and has been used to evaluate responses to various pneumococcal conjugate vaccines (Marchese 2009, Goldblatt 2011, Feyssaguet 2019, and Nolan 2020).

The immune responses (as assessed by OPA and IgG assays) against the 20 polysaccharide antigens common to PCV20 and VAX-24 (1, 3, 4, 5, 6A, 6B, 7F, 8, 9V, 10A, 11A, 12F, 14, 15B, 18C, 19A, 19F, 22F, 23F and 33F) will be compared in the various treatment groups (VAX-24 at 3 different dose levels, and the comparator vaccine), and the 4 incremental polysaccharide antigens contained in VAX-24 (2, 9N, 17F and 20B) will be evaluated separately.

Immunogenicity samples will be collected for subjects aged 50 to 64 years only.

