### 9.4 Populations for Analysis

**Randomized Population:** All screened subjects who provide informed consent, provide demographic and other Baseline Screening measurements, are randomized, and are assigned a study subject ID (number). Each subject will be analyzed as randomized (ie, according to the vaccine regimen to which the subject was randomized).

**Exposed Population:** All subjects who receive at least one study vaccination.

**Safety Population:** All subjects in the Exposed Population who provide safety assessment data. This generally includes any subjects not lost to follow-up at Day 1, as they will be at risk for reporting an SAE. Each subject will be analyzed as treated (ie, according to the vaccine regimen a subject received, rather than the vaccine regimen to which the subject may have been randomized).

**Immunogenicity Evaluable Population:** For this Phase 1/2 study, the immunogenicity population will be analyzed as treated (ie, according to the vaccine regimen a subject receives, which may be different from the vaccine regimen to which the subject is randomized in the case of treatment errors). The Phase 1 subjects aged 18 to 49 years are not included in this population.

The Immunogenicity Evaluable Population (IEP) includes all subjects in the Exposed Population who:

- Have no major protocol deviation that would impact immunogenicity assessment or other reason to be excluded as defined prior to unblinding or analysis.
- Have not received a prohibited medication or vaccine.
- Provide evaluable serum sample results for baseline, the relevant post-vaccination time points, and within the required time frames:
  - Baseline: Day 1 or within 30 days before study vaccine administration
  - Day 29: Day 26 through Day 34, inclusive

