4. ANALYSIS SETS

4.1. Analysis Set Definitions

The following Analysis sets will be evaluated and used for presentation and analysis of the data:

- **Screened Population**: Includes all screened subjects who provided informed consent and were assigned a study subject number, regardless of whether the subject was randomized or not. This population will be used to account fully for subject disposition, starting with the informed consent. The screened population will not be analyzed as such but will be available in the clinical database.
- **Randomized Population (RND)**: Includes all subjects from the Screened Population who consented, provided demographic and other Baseline Screening measurements, and were randomized. Each subject will be analyzed as randomized.
- **Exposed Population (EXP)**: Includes all subjects from the Screened Population who received at least one study vaccine administration. Each subject will be analyzed as treated.
- **Safety Population (SAF)**: Includes all subjects in the Exposed Population but excluding subjects lost to follow up at Day 1 reporting no solicited or unsolicited AEs. Each subject will be analyzed as treated.
- **Immunogenicity Evaluable Population (IEP)**: Includes all subjects in the Exposed Population who:
 - Had no major protocol deviation that would impact immunogenicity assessment or other reason to be excluded as defined prior to unblinding or analysis.
 - Had not received a prohibited medication or vaccine. Identification of subjects receiving prohibited medications will be done via a medical review from the Sponsor of a listing of all concomitant medications.
 - Provided evaluable serum sample results for baseline, the relevant post-vaccination time points, and within the required time frames:
 - Baseline: Day 1 or within 30 days before first study vaccine administration
 - Day 29: Day 26 through Day 34, inclusive

Each subject will be analyzed as treated.

“As randomized” means according to the vaccine regimen to which the subject was randomized, while “as treated” means according to the vaccine regimen a subject received, rather than the vaccine regimen to which the subject may have been randomized.

The RND will be used for the analysis of exposure.

The SAF will be the primary set for the analysis of the safety parameters.

The IEP will be the primary set for the immunogenicity analysis, with the EXP set as supportive.

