6.3.2. Demographic Characteristics

Demographic characteristics at enrollment (i.e., at the time of informed consent) will be presented. Summary will include the following: age, sex, ethnicity, race, height, weight, body mass index.

Medical history will be coded using Medical Dictionary for Regulatory Activities (MedDRA) and summarized alphabetically by System Organ Class (SOC) and Preferred Term (PT).

Childbearing potential and method of contraception will be presented in Listings only.

Table summaries to be produced by treatment group and overall and repeated for the following:

Populations: RND, SAF, IEP

Subgroups: 18-64, 18-49, 50-64

Demographic characteristics and medical history data will also be provided in data listings on the Randomized Population.

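### SAP 4.2 uses the deviation flag IEPEXCL as the only means of exclusion from the IEP, which cannot enforce the serum requirement in SAP 4.1 or the protocol's exclusion of Phase 1

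*SAP*

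**What the plan says.** **Definition.** SAP 4.1 builds the IEP from exposed subjects who, among other conditions, "Provided evaluable serum sample results for baseline, the relevant post-vaccination time points, and within the required time frames". The Day 29 window is Day 26 through Day 34. Protocol 9.4 has the same serum condition and adds: "The Phase 1 subjects aged 18 to 49 years are not included in this population". The SAP definition does not carry that sentence over, although SAP 7 declares no changes from the protocol's analyses.

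**Derivation.** Under SAP 4.2 the sponsor adds two columns to the exported deviation file. Of the first, IEPEXCL, it says "This column will be filled for each PD with" Yes or No; the second gives a reason where the answer is Yes. The section then argues: "Since prohibited medication/vaccine, immunogenicity samples taken out of window, and other major PDs will be recorded as PD" and classified as exclusionary, "only the variable IEPEXCL will be used by" the programming group "to identify subjects excluded from IEP".

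**Who is sampled.** Protocol 5.6.3: "Immunogenicity samples will be collected for subjects aged 50 to 64 years only". SAP 3.3 agrees.

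**Where the IEP is tabulated.** SAP 6.3.2 asks for demographic and medical-history summaries for "Populations: RND, SAF, IEP", each in the subgroups 18-64, 18-49 and 50-64, with no exception for the IEP. SAP 6.6 runs the immunogenicity analyses in 50-64, 50-59 and 60-64 only.

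**The concern.** The definition has a positive condition, that evaluable results exist, while the derivation has only a negative one, that no deviation was flagged. The two agree only if every subject without evaluable serum also has an exclusionary deviation on file. SAP 4.2's justification covers prohibited treatment, mistimed samples and other major deviations, but says nothing about results that are absent or not evaluable.

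The documents themselves foresee such cases without a deviation. Phase 1 subjects have no planned immunogenicity sample. Consent may be withdrawn at any time (Protocol 5.19), and discontinuation before Day 29 has its own visit (Protocol 6.2). Lost or damaged shipments are anticipated (Protocol 5.6.1, Table 3 notes).

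The IEP is the primary immunogenicity set. If its derivation departs from its definition, the reported IEP size and baseline tables include people who contribute no antibody data. The listing of reasons for IEP exclusion (SAP 6.3.1) also has no source field for anyone excluded for a cause other than a deviation.

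**Working it through.** **1. The plan's own total.** Inputs: 16 per arm in Phase 1 and 200 per arm in Phase 2 (SAP 2.3; Protocol Table 4).

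4 × 16 + 4 × 200 = 64 + 800 = 864, which reproduces the total in Protocol Table 4. Neither document states an expected IEP size.

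**2. Largest possible IEP under each rule** (planned numbers, all vaccinated, no other exclusions).

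- Definition (SAP 4.1, Protocol 9.4): at most 800, or 200 per arm, none aged 18 to 49.
- IEPEXCL alone: up to 864, or 200 + 16 = 216 per arm.
- Excess: 864 − 800 = 64, which is 64/864 = 7.4% of the inflated set, or 64/800 = 8.0% on top of the correct one.

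**3. Adding Phase 2 subjects without evaluable serum.** The documents give no rate, so 0% to 10% of 800 is an assumption. The outcome depends on how many of these subjects have a deviation flagged Yes; the table shows both extremes.

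| Assumed share without evaluable serum | IEP by definition | Flag only, none flagged (excess) | Flag only, all flagged (excess) |
|---|---|---|---|
| 0% | 800 | 864 (64) | 864 (64) |
| 2% | 784 | 864 (80) | 848 (64) |
| 5% | 760 | 864 (104) | 824 (64) |
| 10% | 720 | 864 (144) | 784 (64) |

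**4. Which of these subjects can reach an estimate.** Nothing is imputed (SAP 6.2.6, 6.6.1).

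- Phase 1 subjects: none. They have no titers, and SAP 6.6 analyzes only ages 50 to 64.
- Phase 2, no Day 29 result: none. The dependent variable is missing in every GMT, GMC and GMFR model.
- Phase 2, Day 29 result but no evaluable baseline, and no exclusionary deviation: these enter the ANOVA of Day 29 titers, which Protocol 9.7.1 names as the primary model. They cannot enter the ANCOVA, which needs the baseline covariate, or the GMFR models, which need the fold ratio. Under SAP 4.1 they should not be in the IEP ANOVA at all.

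Only the last group matters for estimates.

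**The case against.** The strongest reply is that SAP 4.1 defines the set and a subject without serum never meets it. The IEPEXCL sentence sits under the deviations heading, in the bullet on the reason column. It may mean only that, of the two new columns, the flag and not the reason drives deviation-based exclusions. That reading is possible, but the sentence speaks of exclusion from the IEP without limit and gives a reason why nothing else is needed. A programmer who follows it produces a set that breaks the definition.

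A reader might infer that the SAP intends to count the 64 Phase 1 subjects. The documents do not support this: Protocol 9.4 excludes them by name, SAP 4.1 requires serum they never give, and SAP 6.6 is confined to ages 50 to 64. The 18-49 entry in SAP 6.3.2 may simply be a subgroup list shared by three populations, in which case that IEP table would be empty. The 64 is therefore what the literal rule yields, not the plan's intent.

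A reader might also blame this rule for ANOVA and ANCOVA running on different subjects serotype by serotype. That does not follow. SAP 4.1 states evaluability per subject, not per assay and serotype, so such gaps could arise even if the IEPEXCL rule were deleted.

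Two further points stand in part. Serum on Day 1 and Day 29 is scheduled, so some missed samples will be logged and flagged as deviations, and backup consignments reduce losses in shipment. And SAP 6.3.1 tabulates set sizes and lists membership, so an error could be noticed. However, SAP 2.7 keeps individual listings out of the Day 29 delivery, so the listing would not help at that stage.

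**Conclusion.** The point holds as a contradiction between definition and derivation: SAP 4.2, followed as written, yields a set that SAP 4.1 and Protocol 9.4 do not allow. On planned numbers with everyone vaccinated, the IEP could reach 864 instead of at most 800. Any further excess depends on an unstated rate of non-evaluable serum and on how many such cases are flagged.

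The consequence is mainly descriptive: IEP counts, the analysis-set table, and the demographic and medical-history tables. The one route into the GMT and GMC estimates is a Phase 2 subject with a Day 29 result, no evaluable baseline and no exclusionary deviation. That group is probably small, and nothing in the documents suggests that it would distort the comparison of dose levels with PCV20. The correction is still worth making, because the IEP is the primary immunogenicity set and its membership should follow from one rule fixed before the interim lock.

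**What to change.** - **SAP 4.2:** replace the flag-only sentence. Derive the IEP as exposed subjects aged 50 to 64 with no deviation row marked IEPEXCL = Yes and, from the assay data, an evaluable baseline result and an evaluable result from Day 26 through Day 34. Record a reason for exclusions that come from the assay data, so that the SAP 6.3.1 listing is complete.
- **SAP 4.1:** restore the protocol's statement that Phase 1 is outside the IEP.
- **SAP 6.3.2:** limit the IEP tables to ages 50 to 64.

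Whether to require evaluability separately by assay and serotype is a different choice and is not part of this correction.

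The cost is SAP wording and a few lines of derivation code on data already held, settled before the interim database lock. The downside is that the reported IEP N may be slightly smaller.

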5. DATA HANDLING

5.1. Computing Environment

All descriptive statistical analyses will be performed using SAS statistical software (Version 9.4), unless otherwise noted. Medical History and adverse events will be coded using Medical Dictionary of Regulatory Activities (MedDRA) version 24.1. Concomitant medications will be coded using B3 World Health Organization (WHO) Drug Global (September 2021).

5.2. Data Conventions

The following conventions will be used:

- **Period definition:**
 - **Screening Period:** The period prior to Day 1 visit.
 - **Treatment and Observation:** The period from date of vaccine administration to Day 29 visit.
 - **Follow-up:** The period from Day 29 to Month 6 visits.
- **Visits:**
 - **Study day 1:** The date of study vaccine administration.
 - **End of Treatment Visit:** The Day 29 visit, or the early discontinuation visit for subjects who withdraw study prior to Day 29.
 - **End of Study Visit:** The last recorded visit date.
 - **Unscheduled visits:** Unscheduled visits results will be listed, but not included in tables or graphs. Rules to map unscheduled visit to analysis visit are defined in Section 5.5.
- **Conversion factors (for derived data calculations):**
 - 1 month = 30.4375 days
 - 1 week = 7 days
- **Baseline characteristics and change from baseline:**
 - Weight values recorded in pounds will be converted to kilograms using the following formula: kilograms = pounds/2.2046.
 - Height values recorded in inches will be converted to centimeters using the following formula: centimeters = inches*2.54.
 - Duration on study (weeks) = (Last visit date – randomization date + 1) / 7.
 - (Absolute) Change from baseline = Value at the time point – Baseline value.

- **Adverse events:**

- **Solicited Adverse Events** will be analyzed using the nominal visit (i.e. the page) on which they were recorded and not according to the date they were entered.
- **Solicited Adverse Events continuing beyond 7 days:** Solicited AEs continuing beyond 7 days will be reported in the “Adverse Events (Unsolicited)” page as per Case Report Form (CRF) Completion guidelines and will be identified programmatically as all unsolicited adverse events with answer ‘Yes’ to the question ‘Was this adverse event continuing as reported on the Day 7 subject diary?’.

- **Immunogenicity:**

[figure not shown]
- **GMC [or GMT]:** The geometric mean concentration (or titer) = antilog (LSMeans [log10 x]), where x is the assay result and LSMeans is the least square means calculated by the model.
- **GMR:** The geometric mean ratio = antilog (LSMeans [log10 x]) / antilog(LSMeans [log10 y]), where x and y are the 2 assays results and LSMeans is the least square means calculated by the model.
- **Fold Ratio:** The ratio between titer/concentration at Day 29 visit and the one at Day 1.
- **GMFR:** The geometric mean fold ratio = antilog (LSMeans [log10 y]), where y is the assay fold ratio and LSMeans is the least square means calculated by the model.
- **4-fold increase:** A subject achieved 4-fold increase if fold ratio ≥ 4
- **BLQ:** Below lower limit of quantification (LLOQ). Per Center for Biologics Evaluation and Research (CBER) criterion, BLQ titer/concentration will be analyzed as:
 - 0.5*LLOQ for calculations of GMT/GMC and GMT/GMC Ratios (GMRs)
 - 1*LLOQ for calculations of fold ratio.
- **ULOQ:** Upper limit of quantification. Titer/Concentration above ULOQ will be analyzed as:
 - 1*ULOQ for all calculations (GMT/GMC, GMRs, fold-ratio)

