### 3.3 Estimated Study Duration

The Screening period is 30 days, treatment and observation period is from Day 1 to Day 29, and the follow-up period is through Day 180 (6 months from study vaccination). The maximum possible study duration for an individual is 210 days.

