#### **6.1.6 Months 3, 4, 5, 6 (90 to 180 days after Day 1 ( $\pm$ 5 days))**

These visits are follow-up phone calls for safety evaluation. The following procedures will take place at each visit:

- SAE, NOCI, and MAAE evaluation
- Concomitant medications or vaccines potentially related to SAE, NOCI, MAAE, or prohibited medications

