##### **7.5.1 Reporting Periods**

The four reporting periods for solicited AEs begin immediately after study vaccine administration and continue for 7 days after the injection. The reporting period for unsolicited AEs is immediately after study vaccine administration on Day 1, continuing through Day 29. AEs that correspond to solicited AE terms but occur outside of (or continue past) the solicited AE collection periods are also collected through the unsolicited AE reporting periods. The reporting period for SAEs begins at the time of informed consent and continues for the duration of study participation.

A summary of the reporting periods is presented in [Figure 3](#).

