3.2. Safety Variables

Safety assessments performed during the study included solicited AE up to Day 8 and monitoring of unsolicited adverse events, physical examinations, measurement of vital signs, clinical laboratory evaluations including hematology, serum chemistry, and urinalysis.

The primary endpoints are:

- Percentage of subjects reporting solicited local reactions within 7 days after vaccination (redness, swelling, and pain at injection site) in each age group.
- Percentage of subjects reporting solicited systemic events within 7 days after vaccination (fever, headache, fatigue, muscle pain, and joint pain) in each age group.
- Percentage of subjects reporting unsolicited AEs within 1 month after vaccination in each age group.
- Percentage of subjects reporting SAEs, NOCIs, and MAAEs within 6 months after vaccination.

The secondary endpoint related to Safety assessments is:

- Percentage of participants with laboratory value abnormalities and/or potentially clinically significant laboratory values at 1 month after vaccination.

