6.5.1.2. Unsolicited Adverse Events

An unsolicited AE is an AE that is spontaneously reported by the subject or discovered by the Investigator. New onset of chronic illness(s) would be recorded as part of the collection of unsolicited AEs as specified in the visit procedures. Unsolicited AEs are collected separately from solicited AEs.

Solicited AEs continuing beyond 7 days will be flagged using rules given in Section 5.2 and described in separate summaries as explained in Section 6.5.1.3.

The definition of a treatment emergent AE (TEAE) is an event that occurs after vaccination and within the 28 days after vaccination (i.e., excluding those after a subject has given informed consent, but before vaccination):

- Onset (days) = Start date of AE – Date of Study Vaccine Administration + 1
- An AE is a TEAE if:
 - Onset \geq 1 and Onset \leq 28
 - For AEs with Onset=1 the time of onset of AE must be greater or equal to the time of vaccination to be considered a TEAE

Adverse events are summarized by subject, therefore, in any tabulation, a subject contributes only once to the count for a given adverse event (SOC or preferred term).

Unsolicited AEs will be coded using the Medical Dictionary for Regulatory Activities (MedDRA) and will be summarized by decreasing frequency of SOC and preferred term within SOC in the control group, as follows:

- [P] Any unsolicited TEAEs
- Possibly or probably related unsolicited TEAEs
- Unsolicited TEAEs leading to study withdrawal
- Any AE leading to death
- [P] Any SAE within 6 months after the vaccination by maximum relationship to study treatment. This summary will include serious solicited AEs.
- [P] Any NOCI within 6 months after the vaccination by maximum relationship to study treatment.
- [P] Any MAAEs within 6 months after the vaccination by maximum relationship to study treatment.

Following by-subject Listings will be provided:

- Pre-vaccination AEs (non-emergent)

- All unsolicited TEAEs
- All Serious post-vaccination AEs, NOCIs and MAAEs

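### An early Day 29 visit leaves the last days of the unsolicited-AE window unasked, and the six-month AE endpoints have neither a closing contact at Day 180 nor an onset cut-off

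*SAP*

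**What the plan says.** - **Collection period.** Protocol 7.5.1: "The reporting period for unsolicited AEs is immediately after study vaccine administration on Day 1, continuing through Day 29".
- **Closing visit.** Protocol 6.1.5 and both schedules of events give the Day 29 visit a window of ±3 days, so Days 26 to 32. SAP 5.2 defines treatment and observation as "The period from date of vaccine administration to Day 29 visit", and Protocol 9.2 also ends the treatment period at that visit. The Day 8 and Day 15 contacts have one-sided windows (+3 days).
- **Later contacts.** For the calls at Months 3, 4, 5 and 6, Protocol 6.1.6 lists "SAE, NOCI, and MAAE evaluation" and related medications. Ordinary unsolicited AEs are not on the list.
- **Endpoint and counting rule.** SAP 3.2 lists as primary: "Percentage of subjects reporting unsolicited AEs within 1 month after vaccination in each age group". SAP 6.5.1.2 computes onset as AE start date minus vaccination date plus 1 and counts an event as a TEAE if "Onset \geq 1 and Onset \leq 28".
- **Six months.** Protocol 3.3: "the follow-up period is through Day 180 (6 months from study vaccination". Protocol 6.1.6 allows each call ±5 days, so the Month 6 call falls 175 to 185 days after Day 1. By Protocol 5.18, that visit and any required safety follow-up complete participation. SAP 3.2 and 6.5.1.2 summarise SAEs, NOCIs and MAAEs over six months and give no onset day at which counting stops.

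**The concern.** An AE percentage over a fixed window assumes that every subject was asked about the whole window. Here the visit that closes the unsolicited-AE window may precede its end, and no later contact asks about the same kind of event. A subject seen on Day 26 with a minor AE on Day 27 is counted as event-free unless the event happens to be volunteered. A visit on Day 31 gives nothing back, because onsets after Day 28 are not counted. On its own, this mechanism can only lower the unsolicited-AE percentage.

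The end of follow-up has a related gap. After a Month 6 call at 175 days, no scheduled contact covers the rest of the six months. After a call at 185 days, events beyond Day 180 may be reported, and nothing in the SAP says whether they count.

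**Working it through.** **Plan's own figure.** SAP 2.2 gives the chance of seeing at least one event among 16 subjects, 1 − (1 − p)^16. For p = 15% this is 92.6% and for p = 10% it is 81.5%, which agrees with the stated 92% and 81%.

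**Days unasked.** Take a visit on Day d to cover onsets through Day d.
- SAP rule (onset Days 1 to 28): a Day 26 visit leaves Days 27 and 28, so 2/28 = 7.1%.
- Protocol rule (through Day 29): it leaves Days 27 to 29, so 3/29 = 10.3%.
- Visits uniform over Days 26 to 32: mean loss (2 + 1)/7 = 0.43 day (SAP rule) or (3 + 2 + 1)/7 = 0.86 day (protocol rule).

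**Effect on the percentage.** The documents give no AE incidence, so the incidence p is assumed over a range, with constant onset hazard. Observed percentage = 1 − (1 − p)^(days covered / window). At p = 20%:
- SAP rule: 1 − 0.8^(26/28) = 18.7%, a loss of 1.3 points.
- Protocol rule: 1 − 0.8^(26/29) = 18.1%, a loss of 1.9 points.

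Loss in percentage points:

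| Assumed incidence | All on Day 26, SAP rule | All on Day 26, protocol rule | Uniform visits, SAP rule | Uniform visits, protocol rule |
|---|---|---|---|---|
| 5% | 0.35 | 0.51 | 0.07 | 0.14 |
| 10% | 0.68 | 0.99 | 0.15 | 0.28 |
| 20% | 1.29 | 1.87 | 0.28 | 0.53 |
| 30% | 1.81 | 2.63 | 0.39 | 0.75 |

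These are slightly high, because they treat every AE in the gap as lost although some would be serious, attended or NOCI and so asked about at Month 3.

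**Detection with 16 subjects.** If all 16 came on Day 26, the probability 1 − (1 − p)^(16 × 26/28) would be 91.1% for a 15% event and 79.1% for a 10% event.

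**Six-month endpoints.** A call 5 days early leaves 5/180 = 2.8% of follow-up unasked. For assumed six-month rates of 1% to 10% this is 0.03 to 0.26 points, from p − [1 − (1 − p)^(175/180)]. A call 5 days late with no cut-off adds the same 0.03 to 0.26 points. With calls uniform over 175 to 185 days, mean loss and mean excess are each 15/11 = 1.36 days.

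**Three descriptions of one window.** Because onset is numbered from 1 on the vaccination day, the SAP's limit of 28 ends 27 days after vaccination. The sentence that introduces the rule in SAP 6.5.1.2 speaks of 28 days after vaccination, which reaches Day 29. Protocol 7.5.1 also runs through Day 29. The SAP formula is one day shorter than both.

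**The case against.** The strongest defence is that collection does not formally stop at the visit. Protocol 7.5.1 runs through Day 29 whatever the visit date, Protocol 9.6.3 says that all unsolicited AEs during the study are recorded, and Protocol 6.3 allows unscheduled visits. The SAP 5.2 line labels a study period; it is not the counting rule. This stands in part: a volunteered event can be recorded, and what is missing is the active question.

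The second defence is size. At 20% incidence and uniform visits, the loss of 0.28 points is about 0.6 subject in an arm of 200. The standard error is √(0.2 × 0.8/200) = 2.8 points there, and 10 points with 16 subjects. This stands in full, and the point rests on the low cost of the remedy.

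A reader might also infer more than the documents support:
- *That all primary AE percentages are affected.* The two solicited endpoints use diary Days 1 to 7, and the Day 8 visit cannot be early.
- *That serious events in the Day 26 to 29 gap are lost.* The Month 3 call asks about SAEs, NOCIs and MAAEs.
- *That the percentages can only be too low.* This holds for the early-visit mechanism alone. A late Month 6 call can add events. Partial AE start dates may be imputed to the first of the month, and the Safety Population drops event-free subjects lost at Day 1; both can raise a percentage.
- *That six months means 182.6 days.* SAP 5.2 does list "1 month = 30.4375 days", but as a conversion for derived data. It is not applied to any endpoint window, and the protocol equates six months with Day 180.
- *That one arm is favoured.* The same windows apply to all arms of a randomized, observer-blind study.

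**Conclusion.** The point holds as a small, avoidable weakness in ascertainment. For the primary unsolicited-AE percentage, subjects seen before the window closes are not asked about up to 2 days under the SAP rule, or 3 under the protocol's. The Day 28 cap prevents any offset from late visits. The plausible understatement is a few tenths of a point. It reaches 1.3 points (SAP rule) or 1.9 points (protocol rule) only if every subject came on Day 26, at an assumed 20% incidence and constant hazard. Neither the incidence nor the spread of visits can be checked from the documents.

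For the six-month SAE, NOCI and MAAE percentages, the missing cut-off and the two-sided call window allow errors of at most about 0.26 points either way for assumed rates up to 10%. No comparison between arms is threatened by design.

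**What to change.** 1. **Protocol 6.1.5 and the schedules of events.** Make the Day 29 AE contact one-sided, not before Day 29, as is already done at Day 8 and Day 15. Days 29 to 32 stay inside the Days 26 to 34 allowed for the Immunogenicity Evaluable Population. The AE data are then complete before the Day 29 interim lock in SAP 2.7. Adding a question to the Month 3 call is weaker: it could come after that lock, and it would ask only early-visit subjects to recall minor events about two months later.
2. **Protocol 6.1.6.** Hold the closing Month 6 call on or after 180 days after Day 1.
3. **SAP 6.5.1.2.** State one onset window for unsolicited AEs, reconciling the formula's limit of 28 with the 28 days after vaccination in the same section and with Day 29 in Protocol 7.5.1. Count six-month events with onset up to Day 180, as the protocol defines six months.

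The cost is two window rules, a short SAP edit and slightly less scheduling flexibility. No visit, subject or assay is added.
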